Clinical Trial Registration PRS Cover Page

Document:

Protocol

Official Title:

Personalized Mobile Intervention to Reduce Exposure to Endocrine Disrupting Chemicals (EDCs) in Women of Child-Bearing Age and Their Partners

NCT Number:

NCT05780047

Document Date:

July 9, 2021

Title of Study: Renown Institute for Health Innovation-Million Marker Detect and Detox Pilot

Principle Investigator: [name]

Co-Investigator: [name]

Study Purpose and Narrative

1. Describe the study background, significance, and purpose/hypothesis/research questions.

The exposome encompasses all of the environmental exposures across one's lifespan¹ and includes toxic chemical exposures from food, water, air, and household and consumer products.² It is the exposome *and* the genome that determines our health.¹ And in fact, environmental factors are responsible for *more than 70% of the risk* of developing chronic diseases.³ Thus, assessing the state of the exposome of the population is a crucial factor in assessing public health and advancing recommendations and regulations.

There are over 85,000 man-made chemicals in use today in the U.S., but only 1% have sufficient safety information.⁴ Individuals come into contact with these chemicals every day through food and products, such as personal care and household products. Many of these products contain endocrine disrupting chemicals (EDCs). Due to their ubiquitousness, impacts on the environment, wildlife, and human health, EDCs have become a major public health concern.⁵ Data from the NHANES has shown that more than 90% of US adults have detectable levels of common EDCs, such as bisphenol A (BPA) and phthalates, in their urine.^{6,7} EDC exposures are particularly concerning for reproductive-aged women. Women are the primary consumers of many personal care products,⁷ and exposures during pregnancy predispose the fetus to adverse health effects later in life.⁴

Exposure to EDCs across the U.S. population is suspected to cause many chronic diseases and disorders, including IQ loss, intellectual disability, attention-deficit hyperactivity disorder, childhood obesity, adult obesity, Type 2 diabetes, cardiovascular and metabolic disease, genital defects, infertility, and mortality from reduced testosterone.^{5,8-10} The economic burden of the diseases caused by all EDC exposure is estimated at \$340 billion in the United States, which is 2.33% of the GDP.¹⁵ In order to mitigate the health impacts and corresponding financial burden of exposures to EDCs, large-scale biomonitoring of populations is crucial for developing Health recommendations and regulations. Further, individuals must have access to an affordable, easy, and rapid way to test their exposures to a wide range of EDCs so that they can reduce their exposures.

Million Marker (MM) is a recent company that offers the first at-home EDC testing kit and environmental exposure journal app. We provide affordable and scalable personalized environmental exposure testing and analysis followed by a tailored intervention program to empower individuals to optimize their health, prevent diseases, and manage existing conditions.

The exposome can be assessed through targeted biomonitoring of exposure biomarkers. Currently, targeted biomonitoring is conducted by the Centers for Disease Control and Prevention (CDC) through the National Health and Nutrition Examination Survey (NHANES).¹¹ As of 2019, 14 states have established their own biomonitoring programs to monitor chemicals of local concern.¹² These programs provide some baseline data;¹³ however, the sample sizes are restricted and no longitudinal data on the same participant is collected.¹⁴ A Million Marker-Renown Institute for Health Innovation (RIHI) collaboration (MM-RIHI) could potentially monitor over 60,000 individuals enrolled in Renown's Healthy Nevada Project (HNP) and provide information such as location, demographic, and lifestyle factors related to the exposome, as well as link the genomic information to the exposomic information of these individuals. These individuals could also be assessed over time to determine longitudinal changes, particularly with interventions in lifestyle changes to reduce exposures. Because the MM kit and app are easy to use, convenient, and non-invasive, a MM-RIHI collaboration could provide ample data with minimal effort and risk.

The HNP is the largest community-based population health study in the world, with more than 60,000 participants. This is twenty times larger than NHANES, the largest nationwide population biomonitoring cohort. It's also the first population health study to return clinical results to study participants.

The collaboration between the Renown Institute for Health Innovation (RIHI) and Million Marker would 1) increase biomarker collection and discovery and 2) increase the exposure assessment database (both internal and external) conducted among existing and future project participants. The HNP Project would be the largest population environmental biomonitoring program in the world, and also the first one to report back the biomonitoring results. As most of Million Marker's current users are between the ages of 25-44, this collaboration may help the HNP recruit younger participants. For Million Marker, this collaboration would allow us to collect large amounts of samples/data to further improve our existing platform, enable AI-assisted exposure assessment and prediction, and drive long-term value for our users including the HNP participants.

To initiate this collaboration, we are proposing a pilot to offer our service to individuals within the participants in the HNP and/or through the Renown Healthcare system.

The aims of this pilot study are:

- 1) Test the feasibility of offering MM's service to the HNP existing and future participants
- 2) Collect pilot data and assess EDC levels among participants
- 3) Test the usability and perception of MM's service among participants
- 4) Test whether offering MM's service can lead to EDC reduction behaviors among participants

- 5) Utilize pilot study data to prepare for larger research studies and grant applications
2. *Provide a detailed narrative, non-technical description of the project and of the planned activity for the participants and/or data collection.*

This project will assess the EDC exposure of participants, through urine testing and self-administered journals. We will recruit up to 300 people (aged 18-40) from the existing participants from the Healthy Nevada Project. Participants' urine samples will be collected via mail-in kits that will be sent to participants. Participants will follow Million Marker's current user journey that involves the following: 1) users receive MM's test kits in the mail, 2) take a comprehensive 24-hour food and product exposure survey via the MM app, 3) collect their first void urine sample in the morning, 4) send back their samples, 5) view their personalized reports with tailored product recommendations through a secure online portal, 6) make changes to reduce their exposures, 7) test again to track/monitor/confirm EDC levels if any behavioral changes have been made.

Participants can make changes to reduce their exposures according to the recommendations in their personalized reports. Participants will receive a second test kit three weeks after getting their initial reports, and be asked to complete and ship it back within one week after receiving it in the mail. All participants will be offered the second test kits as there will always be room for chemical reduction.

Participants will fill out the System Usability Scale (SUS) to evaluate the usability of the Million Marker app and their experiences (engagement, satisfaction, and retention) upon the recipient of their reports for both rounds of testing.

References:

1. Wild, C. P. Complementing the genome with an 'exposome': the outstanding challenge of environmental exposure measurement in molecular epidemiology. *Cancer Epidemiol Biomark. Prev* **14**, 1847–50 (2005).
2. Wild, C. P. The exposome: from concept to utility. *Int J Epidemiol* **41**, 24–32 (2012).
3. Rappaport, S. M. & Smith, M. T. Environment and Disease Risks. *Science* **330**, 460–461 (2010).
4. Kelley, A. S. *et al.* Early pregnancy exposure to endocrine disrupting chemical mixtures are associated with inflammatory changes in maternal and neonatal

circulation. *Sci Rep* **9**, 5422 (2019).

5. Trasande, L. *et al.* Burden of disease and costs of exposure to endocrine disrupting chemicals in the European Union: an updated analysis. *Andrology* **4**, 565–72 (2016).
6. CDC. Bisphenol A (BPA) Factsheet. *National Biomonitoring Program* https://www.cdc.gov/biomonitoring/BisphenolA_FactSheet.html (2017).

Clinical Trial Registration PRS Cover Page

Document:

Analysis Plan

Official Title:

Personalized Mobile Intervention to Reduce Exposure to Endocrine Disrupting Chemicals (EDCs) in Women of Child-Bearing Age and Their Partners

NCT Number:

NCT05780047

Document Date:

September 7, 2021

Analysis Plan, Sample Size and Power

This effort will be led by Million Marker's chief statistician and data scientist [name].

For our primary hypothesis (Aim 1), we will test and validate this first-of-its-kind mobile EDC reduction program (MM *Detect and Detox* kit) in a prospective longitudinal cohort intervention trial. We hypothesize that participants will have a reduction in EDC exposures after intervention.

Our **outcome variables** are concentrations of urinary metabolites of bisphenols (BPA, BPS, BPF), phthalates (MBP, MEP, MEHP, MEHHP, MECPP), parabens (methyl, ethyl, propyl and butyl paraben) and oxybenzone (BP-3) at baseline (pre-intervention) and second test (post-intervention, after using Million Marker's *Detect and Detox* kit, receiving the rest report with actionable insights). We will examine the distribution and concentrations of each of eight chemical analytes in urine to determine geometric means, medians, percentiles and ranges of exposures. We expect the creatinine-adjusted urinary concentration of these chemicals to be at log-normally distributed. We will compare the geometric means with those reported in the NHANES study. We will include BMI, age, gender, diet, education and household income as **covariates**. Participants' dietary patterns will be captured in the exposure journal prior to sample collection by looking at their consumption of packaged food and times eating out as these are important culprits of EDC exposures. Other covariates have been collected as part of their participation in the Healthy Nevada Project. We will conduct an **intent-to-treat analysis**, such that all participants will be included in the post-intervention analysis. The primary outcomes are the mean pre-post (first and second tests) differences in creatinine-adjusted concentration levels per analyte (i.e., the mean of the within-subject differences in analyte values from baseline/first test to post-intervention/ second test).

In terms of **sample size and power**, an intervention study conducted by Harley et al.³⁷ showed statistically significant reduction in urinary metabolite concentration of similar EDCs pre-post intervention in adolescent girls (n=100). However, we did not find any analyte standard deviations (SDs) reported in Harley et al. We based our power and sample size calculations on the data from Rudel et al.,⁵² a dietary intervention to reduce EDCs (n=20), where the standard deviation of the difference in urinary metabolite concentrations before and after the intervention was 0.4. Our power calculation indicates that a sample size of 100 will provide 80% power to detect a 10% geometric mean difference in concentrations at baseline (pre-intervention) and second test (post-intervention) with a two-sided $\alpha=0.05$.

For our secondary hypothesis (Aim 2), we will assess changes in participants' environmental health literacy, attitudes, knowledge, and behaviors after using MM's products and services. We hypothesize that participants' environmental health literacy, attitudes, knowledge and behaviors will change after using MM's *Detect and Detox* kit and receiving their reports and personalized recommendations. We will first generate summary statistics on participants' responses. Changes will be calculated based on paired values of individual responses. We will analyze percentage changes by individual responses as well as response categories (attitude, knowledge and behaviors). A Chi-square goodness of fit test will be used for pre-post comparisons. For pre-post category comparisons within individual participants, the Wilcoxon rank-sum test will be used to compare the differences.

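### Could listing diet as a covariate remove the diet-driven part of the primary pre-post change?

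*SAP*

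**What the plan says.** All of this is in the SAP, Analysis Plan, Sample Size and Power, unless stated otherwise.

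- **Covariates (Aim 1 paragraph):** "We will include BMI, age, gender, diet, education and household income as" covariates. No model, coding, centring or visit is given. The sentence comes after the descriptive summaries and the NHANES comparison, not next to the primary outcome.
- **Diet:** "dietary patterns will be captured in the exposure journal prior to sample collection by looking at their consumption of packaged food" and how often participants eat out. There are two sample collections, and the text does not say which one supplies the covariate.
- **The other five:** "Other covariates have been collected as part of their participation in the Healthy Nevada Project". Each is therefore one value per person.
- **Primary outcome, per analyte:** "the mean of the within-subject differences in analyte values from baseline/first test to post-intervention/ second test". No covariate appears in this definition.
- **Aim 2:** it is hypothesised that "environmental health literacy, attitudes, knowledge and behaviors will change after using MM's" kit.
- **Protocol, Study Purpose and Narrative, item 2:** participants "take a comprehensive 24-hour food and product exposure survey via the MM app", later "view their personalized reports with tailored product recommendations through a secure online portal", and finally "test again to track/monitor/confirm EDC levels if any behavioral changes have been made". The repeat is described only as a further test; a second food survey is not mentioned separately.

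**The concern.** The programme works by getting people to change what they eat and use, and the SAP itself treats packaged food and eating out as important exposure sources. Diet recorded before the second sample is then a post-intervention variable that may lie on the path from the report to the urinary concentration. Adjusting for it would not sharpen the estimate of the total change. It would replace that estimate with the change not explained by diet, which is a different quantity.

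The Aim 1 paragraph says that covariates will be included and also defines an outcome without them, and it does not say how the two fit together. The risk would be that a diet-adjusted time effect, smaller than the real change, is reported as the primary result for each analyte.

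**Working it through.** **1. The plan's own figure.** Inputs from the SAP's sample-size paragraph are n = 100, SD of the difference 0.4, a 10% geometric mean difference and two-sided alpha 0.05. The scale of the SD is not stated; natural log is assumed. Then δ = −ln 0.9 = 0.1054, SE = 0.4/√100 = 0.04, and power ≈ Φ(0.1054/0.04 − 1.96) = Φ(0.674) = 75.0% (74.2% with the noncentral t). The stated 80% is not reproduced, but that is a separate matter. What counts here is that the inputs are those of a paired comparison with no covariates.

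**2. Algebra.** Write y for the analyte value, x for person-constant covariates and d for diet at each visit:

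y(i,t) = a(i) + τ·t + γ′x(i) + β·d(i,t) + e(i,t), with t = 0, 1.

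Differencing gives Δy(i) = τ + β·Δd(i) + Δe(i). The person-constant terms drop out, and so does first-test diet used as a single value per person. The fitted time effect is

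τ̂ = mean(Δy) − β̂·mean(Δd).

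Visit-specific diet therefore shifts the estimate by −β̂·mean(Δd), which is zero if mean diet does not change.

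**3. Numerical check.** One simulated set of 100 complete pairs, log scale, with half the effect assumed to run through diet:

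| Form of the analysis | Estimate |
|---|---|
| Plain mean of paired differences | −0.0519 |
| Five fixed covariates, centred or as main effects | −0.0519 |
| The same plus first-test diet | −0.0519 |
| Change in diet, centred | −0.0519 |
| Change in diet, uncentred | −0.0183 |
| Visit-specific diet, mixed model | −0.0072 |
| Age, uncentred, in a change-score regression | −0.0943 |
| Gender coded 0/1, in a change-score regression | −0.0637 |
| All five fixed covariates, uncentred | −0.1454 |

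A second simulated set had a paired mean of −0.1000. Visit-specific diet moved it to −0.0526 (a 9.5% reduction became 5.1%), and the shift of 0.0474 equals minus the fitted slope times the mean diet change.

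Two qualifications follow. Any uncentred covariate moves the intercept of a change-score regression, not only diet; that is a coding artefact. With second tests missing in relation to age (85 of 100 pairs, a separate simulated set), the mixed-model estimate went from −0.0635 without covariates to −0.0659 with the five fixed ones. The exact zero needs complete pairs.

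**4. Size if visit-specific diet were used.** The documents give neither β nor the mean diet change, so the share of a 10% reduction that runs through diet is assumed. Adjusted reduction = 1 − exp[(1 − share)·ln 0.9], with the SD held at 0.4 and n = 100:

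| Share through diet | Adjusted reduction | Power |
|---|---|---|
| 0% | 10% | 75% |
| 25% | 7.6% | 51% |
| 50% | 5.1% | 26% |
| 75% | 2.6% | 10% |
| 100% | 0% | 5% |

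The unadjusted paired mean stays at 10% in every row.

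**5. What must happen for the loss to occur.** (a) The journal is repeated before the second sample. (b) Mean packaged-food intake or eating out changes. (c) Diet is entered by visit, or as an uncentred change. (d) That model is reported as primary. The user journey makes (a) likely without stating it. Aim 2 makes (b) plausible, although the reports are described as giving product recommendations and the analytes include parabens and oxybenzone, for which product routes may matter more. Nothing in either document points to (c) or (d).

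**The case for a change.** The strongest case for a change is that the SAP does say the covariates will be included, diet is the one covariate that belongs to the trial rather than to earlier data, and the documents put it on the causal path. This is a single-arm study whose primary result is one contrast per analyte. If adjustment is left open, someone could choose between adjusted and unadjusted results after seeing the data. One or two sentences would close the point at no cost.

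Part of this stands. The covariate sentence is loose, and visit-specific diet would change the quantity being estimated. But the argument is that the SAP fails to rule out a particular model, and that can be said of almost any model not named in a short plan. The primary outcome itself is not left open: it is spelled out as a mean of individual differences. A diet-adjusted time effect does not match that wording, and a reader could see as much from the SAP. The covariates have other natural uses in Aim 1, such as describing exposure levels or exploring who changed. An added sentence would only repeat what the definition already implies.

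**Conclusion.** No change to the plan is needed. This is a gap that an analyst fills sensibly by following the stated definition, which gives the unadjusted mean within-subject change. Including the fixed covariates or first-test diet alters that estimate by exactly 0, given complete pairs and centred or main-effect terms. Only visit-specific diet, or an uncentred change in diet, would make a substantive difference. Its size cannot be derived from the documents and is zero if mean diet does not shift; the tabulated range rests wholly on assumed shares.

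The conclusion assumes that the definition of the primary outcome governs the primary estimate, which is the plain reading. The result in the algebra holds on the raw or the log scale. The choice of scale, the handling of missing second tests and the 80% power figure are separate questions and are not settled here.

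### The primary outcome has no stated log scale and Aim 1 has no named test, yet the trial is powered on a geometric mean ratio

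*SAP*

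**What the plan says.** All the relevant text is under the SAP heading Analysis Plan, Sample Size and Power.

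- **Primary outcome:** "The primary outcomes are the mean pre-post (first and second tests) differences in creatinine-adjusted concentration levels per analyte", explained in parentheses as "the mean of the within-subject differences in analyte values from baseline/first test to post-intervention/ second test". No logarithm, ratio or geometric mean appears in this definition.
- **Distribution:** "We expect the creatinine-adjusted urinary concentration of these chemicals to be at log-normally distributed".
- **Geometric means:** planned as descriptive summaries, and "We will compare the geometric means with those reported in the NHANES study".
- **Power:** 100 participants are said to give "80% power to detect a 10% geometric mean difference in concentrations" at two-sided 0.05. The input is that "the standard deviation of the difference in urinary metabolite concentrations before and after the intervention was 0.4", with no unit or log base.
- **Aim 1 analysis:** the SAP gives a covariate list, an intent-to-treat statement and an alpha, but no test or model. The only tests it names, a chi-square goodness-of-fit test and a Wilcoxon rank-sum test, are for the Aim 2 questionnaire responses. The Protocol has no statistical analysis text.

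**The concern.** The outcome is worded as a difference in values, while the power target is a ratio. Nothing in the SAP links the two.

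Three things follow.

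1. **Estimand.** A mean raw difference is driven by the most exposed participants. It matches the percentage change the trial was sized for only if everyone changes by the same proportion.
2. **Power.** With log-normal data, a paired t-test on raw differences has less power than one on log differences.
3. **Pre-specification.** Either scale is acceptable for type I error if fixed in advance. A scale left open can be chosen after the data are seen, and that raises the error rate for each analyte.

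**Working it through.** **1. The plan's own figure.** Inputs from the SAP: n = 100, power 80%, two-sided alpha 0.05, SD of the difference 0.4, a 10% geometric mean difference. For paired data, n = (SD × (z₀.₉₇₅ + z₀.₈₀) / δ)², with z₀.₉₇₅ + z₀.₈₀ = 1.960 + 0.842 = 2.802. For example, with δ = −ln 0.90 = 0.1054: (0.4 × 2.802 / 0.1054)² = 113.1, so 114.

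| Reading of the 10% | δ | n for 80%, normal / t | Power at n = 100, t |
|---|---|---|---|
| fall, natural log | 0.1054 | 114 / 116 | 74.2% |
| rise, natural log | 0.0953 | 139 / 141 | 65.5% |
| δ taken as 0.10 | 0.1000 | 126 / 128 | 69.7% |
| fall, log10 | 0.0458 | 600 / 602 | 20.5% |
| rise, log10 | 0.0414 | 733 / 735 | 17.6% |

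No two-sided reading gives n = 100. The only match is a one-sided 0.05 test with δ = 0.10: (0.4 × 2.486 / 0.10)² = 98.9, so 99. That contradicts the stated two-sided alpha. On natural logs, 80% power at n = 100 (t) corresponds to a 10.7% fall, or to an SD of 0.372 for a 10% fall. On log10 it corresponds to a 22.9% fall.

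**2. Raw against log differences.** Model: ln Y₁ = b + e₁ and ln Y₂ = b + ln 0.9 + e₂, with Var(e₁) = Var(e₂) = 0.08, so the SD of the log difference is √0.16 = 0.4. With total log SD S, the pre-post log correlation is 1 − 0.08/S². S is not in the documents, so a range is shown. Assumptions: 100 pairs, a uniform 10% fall, no values below detection, paired t-test, 60,000 simulated trials per row.

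| S (assumed) | Implied correlation | Raw-scale power | Type I error if whichever of raw or log is significant is reported |
|---|---|---|---|
| 0.28 | 0 | 72.4% | 5.8% |
| 0.34 | 0.3 | 71.1% | 6.1% |
| 0.40 | 0.5 | 69.4% | 6.4% |
| 0.50 | 0.68 | 65.4% | 6.9% |
| 0.75 | 0.86 | 54.5% | 7.5% |
| 1.00 | 0.92 | 42.5% | 7.8% |
| 1.25 | 0.95 | 31.6% | 7.5% |

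Log-scale power is about 74% in every row. With the raw scale fixed in advance, type I error at S = 0.5 to 1.25 is 3.9% to 5.0%, so it is not inflated. The raw test reaches 80% power at about n = 140, 190, 280 and 445 for S = 0.5, 0.75, 1.0 and 1.25.

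**3. What each scale estimates.** Let the log change vary by c per SD of usual exposure, with the geometric mean falling 10%. The ratio of arithmetic means is then 0.9 × exp(((s + c)² − s²)/2), where s = √(S² − 0.08). Over S = 0.5 to 1.25:

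- c = 0: 0.900, so the two scales agree.
- c = −0.1 (larger falls in the more exposed): 0.868 to 0.801, a change of −13% to −20%.
- c = +0.1: 0.943 to 1.022, a change of −6% to +2%.

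The slope of 0.1 is assumed and serves only to show that the two estimands can differ.

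**The case against.** The best defence is that the intention is clear. A percentage difference in geometric means is a ratio, the SAP expects log-normal data, and it already plans geometric means. On that view this is an omitted word, not a plan to analyse raw differences. The point about intention is fair. But the parenthesis in the outcome definition is the sponsor's own clarification and it speaks of values, no Aim 1 test is named, and the scale of 0.4 stays open.

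The second objection concerns size. The large power losses need pre-post correlations of 0.68 or more; at 0.5 or less the loss is about 2 to 5 points. The type I error figures assume a selective choice that nothing in the documents suggests. Both points stand, and the figures are illustrations only.

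Third, the Protocol allows up to 300 recruits. With 300 complete pairs under the same model, log-scale power is 99.5%, and raw-scale power is about 98%, 94%, 83% and 66% at S = 0.5, 0.75, 1.0 and 1.25. However, 300 is a ceiling, and the SAP makes its power claim at 100.

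Fourth, a paired t-test uses complete pairs, while the intent-to-treat statement includes everyone, and a mixed model on logs would also be valid. That is true. Complete pairs are, however, already implied by the sponsor's within-subject outcome, and the choice between the two models is secondary to fixing the scale.

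**Conclusion.** The concern holds and should be fixed. The primary outcome has no stated scale, Aim 1 has no named analysis, and the power statement concerns a ratio that the outcome definition does not mention. This conclusion rests on the text and needs no simulation.

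The size depends on what is assumed. If 0.4 is a natural-log SD, power at n = 100 for a 10% fall is about 74%, not 80%; if it is a log10 SD, about 21%. Following the outcome literally lowers power further, by anything from a couple of points to more than half of it, depending on a total log SD that the documents do not give. Type I error is at risk only if the scale is chosen after the data are seen.

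**What to change.** - Define the primary outcome for each analyte as the mean within-subject difference in ln(creatinine-adjusted concentration), second test minus first.
- Name the analysis: a paired t-test on the ln differences, reported as a geometric mean ratio (percent change) with 95% CI. Keep raw differences descriptive.
- If covariates are used, regress the ln difference on baseline values only, mean-centred so that the intercept remains the mean change. Take diet from the first-test journal. The SAP says "dietary patterns will be captured in the exposure journal prior to sample collection", and the Protocol's user journey has participants "make changes to reduce their exposures, 7) test again to track/monitor/confirm EDC levels", so second-test diet may be part of the intervention's effect and should not be adjusted away.
- State the scale of 0.4 and restate the power. On natural logs, n = 100 gives about 74% for a 10% fall, and 80% needs n = 116, a 10.7% fall or an SD of 0.37. On log10, n = 100 gives about 21%, and 80% only for a 22.9% fall.
- Add one sentence on how values below the detection limit enter the log analysis.

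The cost is a few SAP sentences and a somewhat less favourable power figure if 0.4 is on natural logs. No new participant data are needed, and n = 116 is within the Protocol's recruitment ceiling of 300.

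### The SAP's 80% power at a sample size of 100 does not follow from its own inputs, and the 100 is neither defined as recruits or pairs, nor tied to the ceiling of 300, nor adjusted for unreturned second kits

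*SAP*

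**What the plan says.** The only recruitment figure is in the Protocol, Study Purpose and Narrative, item 2: "We will recruit up to 300 people (aged 18-40) from the existing participants from the Healthy Nevada Project". The same item describes a mail-based sequence: first kit, app survey, urine return, report, then a second kit three weeks after the report, with return requested within a week of receipt. Every participant is offered the second kit. No return rate is given.

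The only sample size in the SAP (Analysis Plan, Sample Size and Power) is 100: "Our power calculation indicates that a sample size of 100 will provide 80% power to detect a 10% geometric mean difference", at a two-sided 5% level. The variability comes from a dietary intervention study of 20 people, in which "the standard deviation of the difference in urinary metabolite concentrations before and after the intervention was 0.4". The scale of that 0.4 is not stated, nor is the direction of the 10%.

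The primary outcome, per analyte, is "the mean of the within-subject differences in analyte values from baseline/first test to post-intervention/ second test". The SAP calls the analysis intent-to-treat, "such that all participants will be included in the post-intervention analysis", and gives no method for a participant who has no second test.

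**The concern.** A paired power calculation counts complete pairs. A participant who never returns the second kit contributes no within-subject difference, so the size that matters is the number of people with both results. The plan does not give that number. It gives 100 without a unit in one document and a ceiling of 300 in the other, with nothing to connect them.

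The power sentence is what a reader, funder or later grant application would use to judge what a null or small result means. If 100 is the number of recruits, any loss lowers power below the stated level. If recruitment approaches 300, the study can detect a smaller change than stated. And if 100 is the number of complete pairs, the sentence should at least reproduce from its own inputs.

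**Working it through.** **Inputs.** From the SAP: SD of the paired difference 0.4, difference 10%, two-sided alpha 0.05, power 80%, n = 100. From the protocol: recruitment ceiling 300. Assumptions of this check: 0.4 is on the natural-log scale, the test is a paired t-test on log concentrations, and 50% to 100% of recruits supply both tests. All figures are for one analyte.

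**Step 1: the SAP's own figure.** A 10% reduction is δ = −ln(0.9) = 0.1054. The normal approximation gives

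n = ((1.960 + 0.842) × 0.4 / 0.1054)² = 7.849 × 0.16 / 0.0111 = 113.1, so 114 pairs.

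The noncentral t distribution gives 116.

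At n = 100, δ√n / SD = 0.1054 × 10 / 0.4 = 2.634. Then 2.634 − 1.960 = 0.674, which is 75% power by the normal approximation and 74% by noncentral t. The stated 80% at 100 is not reproduced.

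**Step 2: other readings of the inputs.**

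| Reading (two-sided 5% unless noted) | n for 80% power, normal (t) | Power at 100 pairs, t |
|---|---|---|
| 10% reduction, δ = 0.1054 | 114 (116) | 74% |
| δ = 0.10 taken directly | 126 (128) | 70% |
| 10% increase, δ = ln(1.1) = 0.0953 | 139 (141) | 66% |
| SD 0.4 on log10 scale | 600 to 733 (602 to 735) | 18% to 21% |
| δ = 0.10, one-sided 5% | 99 (101) | 80% |

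Of the variants tried, only the last returns about 100, and it contradicts the SAP's stated two-sided level.

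**Step 3: power by number of complete pairs.** Noncentral t, SD 0.4, 10% reduction, two-sided 5%. The last column is the reduction detectable with 80% power.

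| Complete pairs | One way to reach it | Power | Detectable reduction |
|---|---|---|---|
| 50 | 100 recruits, 50% complete | 45% | 14.9% |
| 70 | 100 recruits, 70% complete | 58% | 12.7% |
| 90 | 100 recruits, 90% complete | 70% | 11.3% |
| 100 | 100 recruits, all complete | 74% | 10.7% |
| 116 | – | 80% | 10.0% |
| 150 | 300 recruits, 50% complete | 89% | 8.8% |
| 210 | 300 recruits, 70% complete | 97% | 7.5% |
| 300 | 300 recruits, all complete | 99.5% | 6.3% |

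**Step 4: recruits needed for 116 pairs.** 116/0.9 = 128.9, 116/0.7 = 165.7 and 116/0.5 = 232, so 129, 166 or 232 recruits at 10%, 30% or 50% loss. At the ceiling, 116 pairs are still reached with a loss of 1 − 116/300 = 61%.

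**The case against.** The strongest reply is that 300 is a ceiling, not a target. One hundred may be the complete pairs required, with recruitment above that as the margin; 300 recruits still yield 100 pairs at 67% loss. On that reading the documents do not conflict and attrition is covered. Near the ceiling, even 50% loss leaves 89% power, and being able to detect less than 10% harms nobody. The protocol also calls this a pilot with feasibility as its first aim, so kit return is something it can reasonably set out to measure.

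Much of this stands. A reader might infer that 300 and 100 contradict each other, but a ceiling is compatible with a smaller target. A reader might also infer that the power figures are wrong for the study as conducted. Neither document says how many people enrolled or returned a second kit, so that cannot be shown.

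A third tempting inference is that an open enrolment range, with the company both supplying the reports and leading the analysis, allows enrolment to stop on favourable results and so inflates the type I error. Neither document describes an interim test, a schedule of looks or closure based on results. Any error rate computed for that scenario would rest on an invented schedule.

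What the reply does not rescue is the power sentence. Reading 100 as complete pairs is the most favourable interpretation, and it still gives 74%. The pilot label does not remove the point either, because the SAP states a primary hypothesis and a power claim for it.

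**Conclusion.** The point holds as a defect in the stated power and in the definition of the sample size. On the SAP's inputs, 100 complete pairs give about 74% power for a 10% reduction (66% to 74% across readings of the 10%), not 80%. With 100 recruits and 50% to 90% completion, power is 45% to 70%. With 300 recruits and 50% to 100% completion, it is 89% to 99.5%. The plan permits this whole range and does not say where in it the study is meant to lie.

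These figures rest on the 0.4 being a natural-log SD. If it is a log10 SD, at least 600 pairs would be needed, which is beyond the ceiling. If it is on the concentration scale, a percentage difference cannot be converted without a mean that the documents do not give. The completion rates are assumptions.

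The consequence is moderate. On the natural-log reading the existing ceiling leaves ample room for adequate power, so the correction is to what is stated rather than to the design. The documents do not establish a contradiction between 300 and 100, or any inflation of type I error.

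**What to change.** Replace the SAP's power sentence with recalculated power and detectable reduction at the expected number of complete pairs, for example one line each for 100, 116, 150, 210 and 300. State the assumed second-kit return rate, the scale of the 0.4, and whether the 10% is a reduction or an increase. Give one planned enrolment, within the ceiling of 300, in both the protocol and the SAP, and say how it leads to the expected pairs. Relabelling 100 as complete pairs is not enough, because that number still misses 80%.

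The same paragraph should say how a participant without a second test is handled, since the intent-to-treat statement covers everyone while the outcome needs both results.

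The cost is a rewritten paragraph in the SAP and one line in the protocol, with no participants beyond the existing ceiling. The downside for the sponsor is that the stated figure at 100 becomes less favourable.
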